4.1.9 Laboratory Requirements

(Must be done within 7 days prior to randomization)

Hematology	Absolute neutrophils	$\geq 1.5 \times 10^9/L$
	Platelets	$\geq 100 \times 10^9/L$
	Hemoglobin	$\geq 90 \text{ g/L}^*$
Chemistry	Bilirubin	$\leq 1.5 \times \text{ULN}$ (upper limit of normal)**
	AST and ALT	$\leq 2.5 \times \text{ULN}$ $\leq 5.0 \times \text{ULN}$ (if patient has liver metastases)
	Serum creatinine or: Creatinine clearance***	$\leq 1.25 \times \text{ULN}$ $\geq 40 \text{ mL/min}$

$*$ Contact CCTG if exception on medical grounds is appropriate to minimize risk of unnecessary transfusion.
 $**$ If confirmed Gilbert's, eligible provided $\leq 3 \times \text{ULN}$.
 $***$ Creatinine clearance to be measured directly by 24 hour urine sampling or as calculated by Cockcroft and Gault equation below:
 Males: GFR = $\frac{1.23 \times (140-\text{age}) \times \text{weight in kg}}{\text{serum creatinine in } \mu\text{mol/L}}$

4.1.10 Non-sterilized male patients who are sexually active with a female partner of childbearing potential must use male condom plus spermicide while on study and for 6 months after the last dose of durvalumab and tremelimumab, or for 3 months after the last dose of durvalumab alone. Female partners of a male subject must use a highly effective method of contraception throughout this period. See Section 9.3.1 for additional details.

Male patients should also refrain from donating sperm during the study and for 6 months after the last dose of durvalumab and tremelimumab or for 3 months after the last dose of durvalumab alone.

4.1.11 Subjects should not donate blood while participating in this study, or for at least 90 days following the last infusion of durvalumab or tremelimumab.

4.1.12 Patient consent must be appropriately obtained in accordance with applicable local and regulatory requirements. Each patient must sign a consent form prior to enrollment in the trial to document their willingness to participate.

Patients who cannot give informed consent (i.e. mentally incompetent patients, or those physically incapacitated such as comatose patients) are not to be recruited into the study. Patients competent but physically unable to sign the consent form may have the document signed by their nearest relative or legal guardian. Each patient will be provided with a full explanation of the study before consent is requested.

4.1.13 Patients must be accessible for treatment and follow-up. Patients registered on this trial must be treated and followed at the participating centre. This implies there must be reasonable geographical limits (for example: 1 ½ hour's driving distance) placed on patients being considered for this trial. The patient's city of residence may be required to verify their geographical proximity. (Call the CCTG office [contact]) if questions arise regarding the interpretation of this criterion.) Investigators must assure themselves the patients registered on this trial will be available for complete documentation of the treatment, adverse events, and follow-up.

Patients must agree to return to their primary care facility for any adverse events which may occur through the course of the trial.

4.1.14 In accordance with CCTG policy, protocol treatment is to begin within 5 working days of patient randomization.

4.2 Ineligibility Criteria

Patients who fulfill any of the following criteria are not eligible for admission to the study:

4.2.1 Patients with a history of other malignancies requiring concurrent anticancer therapy.

4.2.2 Patients with brain metastases are not eligible.

4.2.3 Active or prior documented autoimmune or inflammatory disorders (including inflammatory bowel disease (e.g. colitis or Crohn's disease), diverticulitis with the exception of diverticulosis, celiac disease or other serious gastrointestinal chronic conditions associated with diarrhea), systemic lupus erythematosus, Sarcoidosis syndrome, or Wegener syndrome (granulomatosis with polyangiitis), rheumatoid arthritis, hypophysitis, uveitis, etc., within the past 3 years prior to the start of treatment. The following are exceptions to this criterion:

- Patients with alopecia.
- Patients with Grave's disease, vitiligo or psoriasis not requiring systemic treatment (within the last 2 years).
- Patients with hypothyroidism (e.g. following Hashimoto syndrome) stable on hormone replacement.

4.2.4 History of primary immunodeficiency, history of allogenic organ transplant that requires therapeutic immunosuppression and the use of immunosuppressive agents within 28 days of randomization* or a prior history of severe (grade 3 or 4) immune mediated toxicity from other immune therapy or grade ≥ 3 infusion reaction.

4.2.5 Live attenuated vaccination administered within 30 days prior to randomization or within 30 days of receiving durvalumab.

4.2.6 History of hypersensitivity to durvalumab or tremelimumab or any excipient. Any previous treatment with a PD1 or PD-L1 inhibitor, including durvalumab or an anti-CTLA4, including tremelimumab.

4.2.7 Patients who have experienced untreated and/or uncontrolled cardiovascular conditions and/or have symptomatic cardiac dysfunction (unstable angina, congestive heart failure, myocardial infarction within the previous year or cardiac ventricular arrhythmias requiring medication, history of 2nd or 3rd degree atrioventricular conduction defects). Patients with a significant cardiac history, even if controlled, should have a LVEF $\geq 50\%$.

4.2.8 Concurrent treatment with other investigational drugs or anti-cancer therapy (except LHRH in patients not surgically castrated).

4.2.9 Patients with serious illnesses or medical conditions which would not permit the patient to be managed according to the protocol (including corticosteroid administration), or would put the patient at risk. This includes but is not limited to:

- History of significant neurologic or psychiatric disorder which would impair the ability to obtain consent or limit compliance with study requirements.
- Active infection requiring systemic therapy; (including any patient known to have active hepatitis B, hepatitis C or human immunodeficiency virus (HIV) or tuberculosis or any infection requiring systemic therapy).
- Active peptic ulcer disease or gastritis.
- Pneumonitis.

5.0 PATIENT EVALUATION FLOWSHEET: PRE-TREATMENT, ON STUDY, AND AFTER TREATMENT

All patients entered on study must be evaluated according to the schedule outlined below with documentation submitted according to the schedule in Appendix IV.

Required Investigations	Pre-study (≤7 days prior to randomization)	Day 1 each cycle, and as clinically indicated	Every 12 weeks after randomization	4 weeks after completion of protocol therapy	3 month follow-up (only required for pts without confirmed PD and ongoing toxicities ¹)	6 month follow-up (required for all patients with confirmed PD)
History and Physical Exam						
Including: height, weight, BSA, performance status, clinical tumour measurements (if applicable)	X	X		X		
Blood pressure, heart rate, temperature	X	X ²		X		
Laboratory Procedures/Assessments³						
CBC, differential, platelets	X	X		X ⁴	X ⁴	
PTT, PT/INR (if on anticoagulants)	X	X		X ⁴	X ⁴	
Serum creatinine, bilirubin, AST, ALT, ALP, LDH, albumin, glucose, amylase ⁵ , lipase ⁵ , electrolytes (potassium, calcium, magnesium)	X	X		X ⁴	X ⁴	
PSA	X ⁶	X ⁷		X ⁸	X ⁸	
TSH ⁹	X	X				
Testosterone (to confirm biochemical castration only)	X					
Radiology^{10,11}						
Chest/abdomen/pelvis CT scan Other scans as necessary to document disease ¹²	X (within 28 days prior to randomization or 35 if negative)		X	X	X	
Bone Scan ^{12,13}	X (within 28 days prior to randomization or 35 if negative)		X	X	X (if positive at baseline and does not yet have confirmed PD)	
Other Investigations						
Urinalysis ¹⁴	X					
LVEF ¹⁵	X (within 28 days prior to randomization)					
Adverse Events	X	Continuously		X	X ¹	
Survival/Anti-cancer Treatment Follow-up						X
Correlative Studies (mandatory)						
Fresh tumour biopsy ¹⁶	X					
Archival Tumour Tissues	X					
Blood Collection	X ¹⁷			X ¹⁸		

footnotes on next page ...

1. Every three months thereafter to follow adverse events felt related until resolved to \leq grade 2.
2. Patients will be monitored before, during and after the first cycle infusion of tremelimumab and durvalumab with assessment of vital signs to be collected \leq 30 minutes prior to start of infusion then every 30 \pm 5 minutes during infusion; a 1-hour observation period is recommended after the tremelimumab. Assessment of vital signs in subsequent cycles is required prior to the start of the infusion, and then as clinically indicated. If no clinically significant infusion reactions are observed during or after the first cycle of tremelimumab+durvalumab therapy, subsequent infusion observation periods can be at the investigator's discretion.
3. Pre-treatment blood draws and physical exams may be done one working day prior to treatment if necessary (e.g. Friday for treatment on Monday, or to accommodate holidays). In order to ensure that nadir counts are not missed, every effort should be made to do interim blood draws within 24 hours of the day specified in the protocol. If a patient shows an AST or ALT $\geq 3 \times$ ULN together with total bilirubin $\geq 2 \times$ ULN, refer to Appendix II for further instructions on cases of increases in liver biochemistry and evaluation of Hy's Law. These cases should be reported as SAEs if, after evaluation, they meet the criteria for a Hy's law case or if any of the individual liver test parameters fulfill any of the SAE criteria.
4. Required at 4 weeks. Then every 3 months thereafter to follow abnormal lab results felt related until resolved to \leq grade 2.
5. It is preferable that both amylase and lipase parameters are assessed. For sites where only 1 of these parameters is routinely measured then either lipase or amylase is acceptable as long as the same one is followed throughout.
6. At least three previous PSA values with the interval between of ≥ 4 weeks, should be recorded for the patient to estimate doubling time as well as one prior to registration.
7. PSA should also be done at the end of the last cycle.
8. All patients at 4 weeks. For patients without PSA progression, repeat every 4 to 8 weeks until progression or until new systemic therapy is initiated.
9. Free T3 and free T4 will be measured if TSH is abnormal.
10. Patients with CR/iCR or PR/iPR or equivocal PD (pseudoprogression)/iUPD should have scans repeated after 4 weeks, but no more than 8 weeks, to confirm response.
11. To ensure comparability, baseline scans and subsequent scans to assess response must be performed using identical technique (i.e. scans performed immediately following bolus contrast administration using a standard volume of contrast, the identical contrast agent, and preferably the same scanner).
12. Maintain schedule every 12 weeks even if cycles are delayed.
13. Bone scan is required and must be repeated every 12 weeks and end of study, regardless if positive or negative at baseline, as well as when clinically indicated. If NEW bone lesion(s) are noted on the patient's bone scan, see Section 8.5.4 for details.
14. Only as clinically indicated after baseline
15. Only if significant cardiac history (see section 4.2.7)
16. Fresh Biopsy is mandatory for all patients after consent but prior to randomization, see Section 12.0.
17. To be collected after randomization and prior to cycle 1 treatment.
18. To be collected at end of treatment/disease progression

5.1 Follow-up for Ineligible or Patients That Go Off Study Prior to Starting Protocol Therapy

The follow-up requirements for ineligible patients/patients who have received no protocol therapy prior to going off study include submission of the Baseline Report plus an End of Treatment Report. Data submission for ineligible participants who have received at least one dose of protocol therapy should be followed according to the protocol to allow for treatment and adverse event assessment.

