8.5 Prostate Response according to PCWG3 *(as defined by Scher 2016)*

All patients will be evaluable for PSA response provided follow-up PSA values are obtained to allow application of the definitions below [Bubley 1999].

Response: 50% fall in PSA from baseline maintained for ≥ 4 weeks, and without evidence of disease progression documented at time of confirmatory values.

Non Response: Failure to achieve PSA response criteria.

PSA response duration will commence on the date of the first 50% decline in PSA. The response duration ends when the PSA value increases by 50% above the nadir value, provided that the increase is at least 2 ng/mL (μ g/L) (or back to baseline).

8.5.1 *PSA Progression*
(as defined by Scher 2016)

In PSA non-responders: PSA progression is defined as the date that a 25% or greater increase and an absolute increase of 2 ng/mL (μ g/L) or more from the nadir (or baseline if no decrease from baseline is documented), which is confirmed by a second value obtained 3 or more weeks later.

In PSA responders: rise in PSA of 25% (minimum 2 ng/ml (μ g/L)) above nadir value and confirmed by a second increasing value obtained 3 or more weeks later.

Time to PSA progression will be calculated from date of randomization to date of PSA progression. If interval PSA values are collected or reported during cycle, only the end of cycle PSA (PSA collected for Day 1) will be used in response evaluation.

NOTE: Because with systemic treatment an initial rise in PSA is followed by a drop, it is recommended patients receive at least 12 weeks of therapy even if PSA is rising, provided no other evidence of progression is seen, palliative radiation is not required and protocol therapy is tolerable (see Section 10.0).

8.5.2 *Clinical Benefit*

Clinical benefit is defined for the purpose of this protocol as one of the following:

- PSA decline \geq 50%
- Complete or partial objective response
- Stable disease for \geq 12 weeks

8.5.3 *Clinical Progression*

Clinical progression is defined as the need for palliative radiotherapy, change in anti-cancer therapy, or cancer related decrease in ECOG performance status to \geq 3.

8.5.4 *Bone Disease Progression*

For the purpose of evaluation of bone disease in this study, a bone scan will be done at baseline and must be repeated every 12 weeks after randomization and at end of study, regardless if positive or negative at baseline.

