For progressive disease in bone lesions, if at least 2 new bone lesions are seen by bone scan on the first post treatment scan, then these lesions are confirmed by a second bone scan done 6 or more weeks later that also shows at least 2 additional new bone lesions (2 + 2 rule) then the date of progression is the date of the first post-treatment scan.

For scans after the first post treatment scan, if 2 new bone lesions are visualized, then these lesions need to be seen on a subsequent scan confirming disease progression. If confirmed, the date of PD is the date of the first scan. In general, unequivocal progression of bone lesions will not be accepted as evidence of disease progression unless the criteria above are met and are confirmed.

Additionally, if a new bone lesion(s) are seen on the patient's CT it will also need to be confirmed with a bone scan and will ONLY be considered PD if the criteria above are met.

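### The 3-month follow-up bone-scan cell excludes baseline-negative patients, contradicting footnote 13 and Section 8.5.4, so some off-treatment bone progression may be missed or dated late

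*Combined protocol and SAP*

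**What the plan says.** The Bone Scan row of the Section 5.0 flowsheet has an unconditional mark in the 12-weekly column and in the column for 4 weeks after therapy. In the next column, headed "3 month follow-up (only required for pts without confirmed PD and ongoing toxicities", the entry becomes "X (if positive at baseline and does not yet have confirmed PD".

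Footnote 13, attached to the label of that row, says: "Bone scan is required and must be repeated every 12 weeks and end of study, regardless if positive or negative at baseline". It adds scans "as well as when clinically indicated". Section 8.5.4 repeats the rule and counts from randomization: scans "must be repeated every 12 weeks after randomization and at end of study, regardless if positive or negative at baseline".

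Section 8.5.4 also sets what counts as bone progression. For scans after the first, "if 2 new bone lesions are visualized, then these lesions need to be seen on a subsequent scan confirming disease progression". For a new bone lesion seen on CT, "it will also need to be confirmed with a bone scan and will ONLY be considered PD if the criteria above are met".

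Section 10.4 follows patients who stop treatment with response, stable disease or unconfirmed progression, and who have not started other systemic therapy, every 3 months until relapse. It refers to Section 5.0 for the tests to be done, so sites are sent to this flowsheet.

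**The concern.** The cell makes the scan conditional on a positive baseline, and the footnote on the same row says in terms that baseline status does not matter. A site cannot satisfy both for a baseline-negative patient in 3-month follow-up.

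The stake is ascertainment. Section 13.1 names bone progression as one basis of the secondary time-to-progression evaluation. Section 8.4 runs response duration and stable-disease duration until progression, not until treatment stops, and responding or stable patients who stop early are the ones who reach this column. If the cell is followed, whether bone progression is looked for depends on a baseline characteristic. If some sites follow the cell and others the footnote, it also depends on the site.

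**Working it through.** The plan states no figure on this point, so the check is a comparison of the texts followed by an illustrative count.

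**1. Which patients are affected.** Baseline bone scan negative, off treatment, no confirmed progression, no other systemic therapy started, and past the 4-week visit. On treatment and at 4 weeks, the scan is unconditional for everyone.

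**2. What each place asks for in these patients.**
- 3-month follow-up cell: no bone scan.
- Footnote 13: bone scan every 12 weeks and at end of study.
- Section 8.5.4: bone scan every 12 weeks from randomization and at end of study.

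The intervals are nearly the same: 12 × 7 = 84 days against 365.25 / 4 = 91.3 days. The conflict is about who is scanned, not how often.

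**3. Which routes to bone progression remain if the cell is followed.**
- Chest/abdomen/pelvis CT stays in the same column with no baseline condition, together with other scans needed to document disease.
- Footnote 13 allows a bone scan on clinical indication.
- A new bone lesion on CT itself calls for a bone scan under Section 8.5.4.

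What is left uncovered is bone progression without symptoms that CT does not show, for example outside the CT field.

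**4. Confirmation after the 4-week visit.** Section 8.5.4 needs a further bone scan before new lesions count. If two new lesions first appear on the 4-week scan of a baseline-negative patient, the cell provides no routine follow-up scan to confirm them. Footnote 10 asks for repeat scans at 4 to 8 weeks for equivocal or unconfirmed progression and might be read to cover this. It does not mention bone scans, and where the 2 + 2 rule applies the second scan must come at least 6 weeks later.

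**5. Primary endpoint.** Sections 8.2.5 and 8.3 (Table 3) classify best response from start to end of treatment, when bone scans are unconditional. The objective response rate is therefore little affected.

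**6. Size.** The documents give neither the baseline-negative proportion nor the proportion stopping without confirmed progression. Assume 20-40% and 10-25%, for illustration only. Enrolment is 24 to 74 (Section 13.1), which is 2 × 12 to 2 × 37 (Section 13.3). Patients affected = N × proportion negative × proportion stopping:
- N = 24: 24 × 0.20 × 0.10 = 0.48, to 24 × 0.40 × 0.25 = 2.4.
- N = 74: 74 × 0.20 × 0.10 = 1.48, to 74 × 0.40 × 0.25 = 7.4.

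These are patients without a routine bone scan in follow-up, not missed progressions, which would be fewer.

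**The case against.** The strongest reply is that the texts can be read together. On that reading footnote 13 and Section 8.5.4 govern the 12-weekly column and end of study, and the follow-up cell deliberately reduces imaging once treatment has stopped. The documents do not exclude this, and they do not define end of study. But footnote 13 sits on the row label, while notes meant for particular columns are marked on the cell elsewhere in the flowsheet (the PSA row, for example). Section 8.5.4 counts from randomization, and neither text limits itself to the treatment period. Conversely, the 12-weekly column is not limited to treatment either, so a site reading the whole row would still find a scan requirement. This makes the matter a contradiction rather than a clear omission.

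A second reply is that little is lost. All patients have measurable disease followed by unconditional CT, and PSA is repeated every 4 to 8 weeks off treatment until progression or new systemic therapy. This stands in part and keeps the residue small. It does not remove it: Section 1.2 lists time to objective progression as its own objective, which PSA does not serve, and CT alone cannot establish bone progression under Section 8.5.4.

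A reader might infer that bone progression in these patients cannot be recorded, or has no route at all. The routes in step 3 of the working show otherwise. Nor do the documents support a minimum delay of one 12-week interval, since a triggered scan can come sooner. A difference between arms would need unequal stopping without progression, which the documents do not give, and it would carry little weight in a trial declared non-comparative.

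**Conclusion.** The contradiction holds, and the cell is wrong as written beside footnote 13 and Section 8.5.4. The consequence is limited: asymptomatic bone progression not seen on CT may be missed or dated late in baseline-negative patients who are off treatment without confirmed progression, and lesions first seen at the 4-week visit may lack a routine confirming scan. The outcomes exposed are time to progression and the durations of response and stable disease.

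The number affected cannot be derived from the documents. The ranges of 0.5-2.4 and 1.5-7.4 patients rest wholly on the assumed proportions, and the upper range applies only if both arms expand fully. The point merits correction because the texts conflict and the correction is small, not because a large bias has been shown.

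**What to change.** Reconcile the three places. The direct way is to delete the baseline condition so that the cell reads: X (all patients without confirmed PD; see footnote 13). The table then agrees with the two places that already require the scans.

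If the sponsor intended the restriction, footnote 13 and Section 8.5.4 should state it, and the analysis of time to progression and of the durations should acknowledge that bone ascertainment off treatment is reduced in baseline-negative patients.

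The first option costs one table cell and adds no scan beyond what footnote 13 and Section 8.5.4 call for. For sites now following the cell, it means one bone scan per 3-month visit for a few patients. The second option costs two sentences of text and a stated limitation.

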7.1.4 Dose Adjustments

The major toxic effects of durvalumab or tremelimumab which are anticipated to limit dosing are hypersensitivity/ infusion related reactions and possible class related immune related AEs, based on the mechanism of action of durvalumab ± tremelimumab leading to T-cell activation and proliferation. Potential immune related AEs include pneumonitis, hepatitis, diarrhea/colitis and intestinal perforation, endocrinopathies (thyroiditis, hypo and hyperthyroidism, adrenal insufficiency, hypophysitis/hypopituitarism diabetes insipidus and Type 1 diabetes mellitus), nephritis, rash/dermatitis, pancreatitis, myocarditis, myositis/polymyositis and rare/less frequent irAEs including neuromuscular toxicities such as myasthenia gravis and Guillain-Barre syndrome. Other inflammatory responses that are rare with a potential immune-mediated etiology include, but are not limited to, pericarditis, sarcoidosis, uveitis and other events involving the eye (e.g. keratitis and optic neuritis), skin (e.g. scleroderma, vitiligo and pemphigoid), hematological (e.g. hemolytic anemia and immune thrombocytopenic purpura) and rheumatological (e.g. polymyalgia rheumatic and autoimmune arthritis) events, vasculitis, non infectious encephalitis or non infectious meningitis. It is possible that events with an inflammatory or immune mediated mechanism could occur in nearly all organs.

The guidelines that outline dose adjustments for these toxic effects can be found in Appendix II. If a patient experiences several adverse events and there are conflicting recommendations, please use the recommended dose adjustment that requires the greatest dose hold or discontinuation. Adverse events will be graded using the NCI Common Terminology Criteria for Adverse Events (CTCAE) (see Appendix V).

Dose adjustments (slowing/interruption of infusion rate, omission of a dose, or permanent discontinuation) will be made for hematologic and other adverse events.

If the infusion cannot be administered, it should be omitted until the next planned infusion.

The next cycle should not be given until the laboratory criteria in Section 4.1.9 are met and resolution of all drug related toxicity to \leq grade 2. Discuss with CCTG if asymptomatic/not felt to be clinically significant.

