8.0 CRITERIA FOR MEASUREMENT OF STUDY ENDPOINTS

8.1 Definitions

8.1.1 Evaluable for adverse events. All patients will be evaluable for adverse event evaluation from the time of their first treatment.

8.1.2 Evaluable for response. All patients who have received at least one cycle of therapy and have their disease re-evaluated will be considered evaluable for response. Patients who exhibit objective disease progression prior to the end of cycle 1 are considered to be evaluable). Patients on therapy for at least this period and who meet the other listed criteria will have their response classified according to the definitions set out below *[Seymour 2017]*.

Response and progression will be evaluated in this study using the revised international criteria (1.1) proposed by the RECIST (Response Evaluation Criteria in Solid Tumours) committee *[Eisenhauer 2009]* as well as the modified iRECIST guidelines *[Seymour 2017]*. Investigators should note the different requirements for confirmatory scans as well as follow up for the two criteria.

See Section 10 for criteria for continuing treatment past RECIST 1.1 disease progression.

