10.4 Follow-up Off Protocol Treatment

All patients will be seen at 4 weeks after completion of protocol therapy. For patients who go off protocol treatment with iCPD, and have ongoing toxicities (until resolved to \leq grade 2) and late toxicities (including second malignancies) follow-up will be required every 3 months.

For patients with no ongoing or late toxicities and have confirmed disease progression, follow-up will be required every 6 months for survival data and other anti-cancer treatment only. For patients who go off protocol treatment with CR/ICR, PR/iPR, SD/iSD or iUPD ongoing, and have not already started other systemic therapy follow-up will be required every 3 months until relapse (see Section 5.0 for investigations to be performed) and then every 6 months until death.

Death Report will be required for all patients, due within 2 weeks of knowledge of death (see Appendix IV - Documentation for Study).

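### No TSH is scheduled after the last dose of an uninterrupted course, although CBC, coagulation, chemistry and PSA are all repeated at the 4-week post-treatment visit

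*Combined protocol and SAP*

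**What the plan says.** In the Section 5.0 flowsheet, TSH is marked at pre-study and in the column headed "Day 1 each cycle, and as clinically indicated". Its cells for the 12-week, 4-week post-treatment, 3-month and 6-month columns are blank. The only footnote on the row is number 9: "Free T3 and free T4 will be measured if TSH is abnormal".

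The other laboratory rows repeated on treatment are handled differently. CBC, coagulation and chemistry are marked at both the 4-week and 3-month columns under footnote 4: "Required at 4 weeks. Then every 3 months thereafter to follow abnormal lab results felt related until resolved" to grade 2 or lower. PSA is also marked in both columns (footnote 8) and has an extra draw under footnote 7: "PSA should also be done at the end of the last cycle".

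Footnote 3 shows that Day 1 bloods belong before the infusion: "Pre-treatment blood draws and physical exams may be done one working day prior to treatment if necessary". Section 7.1.1 sets the cycle at 4 weeks. Section 10.4 states: "All patients will be seen at 4 weeks after completion of protocol therapy". Section 7.1.4 lists among the potential immune-related events "endocrinopathies (thyroiditis, hypo and hyperthyroidism, adrenal insufficiency, hypophysitis/hypopituitarism". Toxicity and tolerability is a secondary objective (Section 1.2), and Section 8.1.1 fixes the safety population: "All patients will be evaluable for adverse event evaluation from the time of their first treatment".

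**The concern.** TSH is the only laboratory test repeated during treatment that has no post-treatment entry. The last scheduled TSH is drawn just before the last infusion, so it says nothing about the effect of that infusion. A patient treated once counts in the adverse-event denominator but has no scheduled TSH after any exposure.

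The protocol otherwise treats the period after the last dose as one of continuing risk. Section 10.4 provides for follow-up of ongoing and late toxicities, and Sections 4.1.10 and 4.1.11 extend the contraception and blood-donation restrictions for months.

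What is at stake is limited to laboratory abnormalities without symptoms. Symptomatic thyroid events should still be recorded, because adverse events are collected continuously on treatment, again at 4 weeks, and every 3 months while related and unresolved. An asymptomatic abnormality that first arises after the last dose can be missed, which would bias the reported thyroid event count downwards. The shortfall matters most for patients who stop after one or two doses.

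**Working it through.** The plan gives no figure for this point, so there is none to reproduce. The check is a reading of the schedule followed by simple arithmetic.

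**Scheduled post-dose TSH tests.** With n uninterrupted doses there are n Day 1 draws, each before its dose. The first precedes all treatment, which leaves n-1 after at least one dose. Adding the 4-week visit gives n.

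| Doses received (n) | Now (n-1) | With a 4-week TSH (n) |
|---|---|---|
| 1 | 0 | 1 |
| 2 | 1 | 2 |
| 3 | 2 | 3 |
| 4 | 3 | 4 |
| 6 | 5 | 6 |

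**Does the Day 1 column already cover the end of the last cycle?** Footnote 7 indicates not: an end-of-last-cycle draw had to be written in for PSA, and nothing similar was written for TSH.

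**Interval from the last scheduled TSH to the 4-week visit.** Counted from the last dose (one reading of the flowsheet column), it is 4 weeks. Appendix IV times the report 4 weeks after the end of the last cycle, which gives 4 + 4 = 8 weeks. The interval is therefore 4 to 8 weeks.

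**Size.** Let p be the chance that a first asymptomatic TSH abnormality arises in one dosing interval. The documents give no value; 1% to 5% is assumed. Take p as constant, let every patient receive n doses and attend the visit, and let an abnormality persist until the next draw.

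- Proportion detected now: 1 - (1-p)^(n-1)
- Proportion detected with the added test: 1 - (1-p)^n
- Gain: p(1-p)^(n-1)

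Multiplying the gain by the 37 patients of a fully expanded arm (Section 13.3) gives the extra patients detected:

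| p | n = 1 | n = 2 | n = 4 |
|---|---|---|---|
| 1% | 0.37 | 0.37 | 0.36 |
| 3% | 1.11 | 1.08 | 1.01 |
| 5% | 1.85 | 1.76 | 1.59 |

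For example, 37 × 0.05 × 0.95^3 = 1.59. If an arm closes after the 12 patients of stage 1, the gain at n = 1 is 12 × 0.01 = 0.12 to 12 × 0.05 = 0.60 patients; at n = 4 and p = 5% it is 12 × 0.05 × 0.95^3 = 0.51.

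**What the added test does not do.** Detection still depends on the number of cycles received. At p = 5%, it rises from 0% to 5.0% at n = 1, and from 1 - 0.95^3 = 14.3% to 1 - 0.95^4 = 18.5% at n = 4.

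**The case against.** Five points can be made on the other side.

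- **Appendix II might require thyroid tests after treatment.** It is only a link to an external guideline and could not be checked. This stands as a limit: the point concerns the flowsheet, which Section 5.0 makes binding for all patients.
- **The comparators serve other purposes.** PSA supports efficacy endpoints, and footnote 3 ties blood counts to nadirs and liver tests to Hy's Law. Different schedules can be deliberate. That is fair, and this is a design choice rather than a contradiction. But thyroid toxicity is also named in the protocol, and no reason is given for stopping its test earlier.
- **n-1 is a minimum.** Treatment runs until progression or unacceptable toxicity, so a patient may have Day 1 bloods drawn and then not be treated, or may be tested because the clinician sees a reason. This stands, but the plan does not guarantee either, and the second depends on suspicion.
- **The size rests on an assumed rate and a simple model.** This stands too. The model counts the gap as one interval although it may last 8 weeks, and at 1% the gain is about 0.4 of a patient per full arm.
- **Three-monthly repeats under footnote 4 add little.** They apply only to related abnormalities above grade 2, which would be unusual for one without symptoms, and related adverse events are already followed under footnote 1. This stands; nearly all the value lies in the single 4-week test.

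None of these supplies a scheduled TSH after the last dose within the flowsheet.

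**Conclusion.** The concern holds. As Section 5.0 is written, an uninterrupted course ends with no scheduled TSH after the last dose, and a patient treated once has no scheduled TSH after exposure. The consequence is possible under-detection of late asymptomatic thyroid abnormalities: about 0.4 to 1.9 patients per 37-patient arm under the assumed 1% to 5% per interval, and at most 0.60 in an arm closed at 12. In arms of this size, one or two events visibly shift a reported rate (1/37 = 2.7%).

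The schedule reading is firm. The size is illustrative, and the conclusion is subject to whatever the external toxicity guideline requires. The objective response rate, sample size and stage decisions are untouched. This is an inexpensive improvement worth making, not a threat to the trial's main conclusions.

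**What to change.** Mark TSH, with reflex free T3 and T4 as in footnote 9, in the 4-week post-treatment column. Attach footnote 4 to the TSH row for consistency with the other safety laboratory tests, accepting that few repeats will follow. Keep all treated patients as the adverse-event denominator, as Section 8.1.1 requires, and report beside each arm's thyroid event rate the number of patients with at least one post-dose TSH, so that readers can see how many were actually tested.

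The cost is one assay per treated patient on blood already drawn at an existing visit: 24 to 74 assays at the enrolment planned in Section 13.1, plus reflex tests and repeats for the few abnormal results. No visit or procedure is added.
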